#### **Analysis methods**

No missing data imputation will be performed. The proportion of patients with 6-month disability progression at the end of study will be presented including associated 95% Clopper Pearson exact intervals.

Disability progression at Visit 1, Visit 2 and Visit 3 will also be presented and derived in the same way. A bar plot with disability progression from Visit 1 to Visit 4 will be presented. Additionally, the results for EDSS, 9HPT and T25FW scores will be presented descriptively by Visit, including an absolute and relative change from baseline and to the previous visit.

## 14.3.2 Sensitivity Analyses of the Secondary Outcome 6-month Disability Progression

Four sensitivity analyses will be performed to assess the robustness of the results of the secondary outcome.

The first sensitivity analysis will be a complete case analysis that will derive disability progression only for cases where it can be determined without reservations, setting all the other cases to missing. This means that if only one or two out of the three assessments are available, disability progression will either be "Yes" if those are sufficient for the assessment or "Missing" if progression criteria are not observed in any of the available assessments. The number of patients included in these analyses will be less than the ones includes in the main analysis.

The second sensitivity analysis will include a Non-responder (NR) missing data imputation. All patients for which disability progression cannot be assessed or is "No" but not all three assessments are available will be set to "Yes".

Both approaches will provide a significant underestimation of the treatment effect due to the anticipated missing data in the optional assessments.

A third sensitivity analysis will be performed using EDSS only for disability assessment derivation.

The fourth sensitivity analysis will replicate the above described third sensitivity analysis but by two subgroups:

- Patients with at least one EDSS score obtained within 3 months following a relapse
- Patients with both EDSS scores obtained more than 3 months following a relapse

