9.1.2.2 Secondary

- Difference in ARR between the pre-baseline 12-month period and over the 12 months period after the start of cladribine (1 year)
- Percentage of patients with 6-month disability progression⁵ at the end of the study followup period (2 years), measured as EDSS, T25FW (optional) and 9-HPT (optional).

⁴ Relapses will be diagnosed by the treating physicians, as per routine clinical practice; a typical definition within this context is the appearance of new symptoms of the exacerbation of pre-existing symptoms that are attributed to MS and occur over a minimum of 24 hours and separated from a previous attack by at least 30 days, in the absence of fever or infection.

⁵ Disability progression is defined as progression on ≥1 of 3 components (EDSS, T25FW, and/or 9HPT) confirmed ≥24 weeks apart and with a ≥20% minimum threshold change for T25FW and 9HPT, Progression on EDSS is defined

L04AA40 MS700568 0070

Cladribine

- Percentage of patients with 6-month disability improvement⁴ at the end of the study followup period (2 years), measured as EDSS, T25FW (optional) and 9-HPT (optional)
- · Occurrence of adverse events and of serious adverse events
- Quality of life (MSIS-29)
- Treatment Satisfaction (TSQM v1.4)
- CCI
- Treatment adherence, assessed as percentage of cladribine tablets taken versus prescribed dose

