# 14.3.1 Secondary Objective: Derivation and analysis of the Secondary Outcome 6-month Disability Progression

#### **Derivations**

Disability progression will be assessed using the Visit 4 data and comparing the results with Visit 3. As per definition, if Visit 4 and Visit 3 dates are not separated by at least 24 weeks, disability progression will be set to missing. Disability progression will be assessed if at least one assessment (EDSS, T25FW or 9HPT) is available. As per definition, disability progression will be derived as "Yes" if at least one of the below cases occur:

- Visit 4 EDSS is ≥1 point greater than Visit 3 EDSS if Visit 3 EDSS is greater than 0;
- Visit 4 EDSS is 1.5 or greater when Visit 3 EDSS is 0;
- 20% increase in the T25FW score (average of the two trials) from Visit 3 to Visit 4;
- 20% increase in the 9HPT score (The two trials for each hand are averaged, converted to the reciprocals of the mean times for each hand and then the two reciprocals are averaged) from Visit 3 to Visit 4.

If none of those cases occurred, disability progression will be set to "No".

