# 14.4.2 Sensitivity Analyses of the Secondary Outcome 6-month Disability Improvement

Four sensitivity analyses will be performed to assess the robustness of the results of the secondary outcome 6-month disability improvement.

The first sensitivity analysis will be a complete case analysis that will derive disability improvement only for cases where it can be determined without reservations, setting all the other cases to missing. This means that if only one or two out of the three assessments are available, disability improvement will either be "Yes" if those are sufficient for the assessment or "Missing" if improvement criteria are not observed in any of the available assessments. The number of patients included in these analyses will be less than the ones includes in the main analysis.

The second sensitivity analysis will include an NR missing data imputation. All patients for which disability improvement cannot be assessed or is "No" but not all three assessments are available will be set to "No".

In this case, it is expected that the complete cases approach will overestimate the true treatment effect while the NR will provide an underestimation of the true treatment effect.

A third sensitivity analysis will be performed using EDSS only for disability assessment derivation.

The fourth sensitivity analysis will replicate the above described third sensitivity analysis but by two subgroups:

- Patients with at least one EDSS score obtained within 3 months following a relapse
- Patients with both EDSS scores obtained more than 3 months following a relapse

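### The 'complete case' disability sensitivity analysis keeps incompletely tested patients who progressed and drops those who did not, so its proportion is biased upward

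*SAP*

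**What the plan says.** Protocol 9.1.2.2 and 8.2 make T25FW and 9HPT optional, done only where routine practice includes them. Protocol 9.7.3 recognises that the resulting gaps could bias the disability analysis and leaves the handling to the SAP.

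The main analysis (SAP 14.3.1, Derivations) compares Visit 4 with Visit 3 and accepts partial data: "Disability progression will be assessed if at least one assessment (EDSS, T25FW or 9HPT) is available". A patient who meets no criterion on whatever was measured is a No.

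SAP 14.3.2 then lists four sensitivity analyses intended to test robustness:

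- **First (complete case).** A patient with one or two of the three tests counts as Yes when those tests are enough to show progression. The same patient is treated as missing "if progression criteria are not observed in any of the available assessments".
- **Second (non-responder, NR).** Patients who cannot be assessed become Yes. So do patients who are No "but not all three assessments are available will be set to" Yes.
- **Third and fourth.** EDSS only, the fourth split by timing relative to a relapse.

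The SAP adds that the first two will substantially understate the treatment effect, but gives no size. For improvement (SAP 14.4.2) the first analysis has the same asymmetry: an incomplete patient is missing "if improvement criteria are not observed in any of the available assessments". The SAP expects this to overstate the effect. The NR rule for improvement works differently: an incomplete No stays No.

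**The concern.** A complete case analysis normally includes patients by data availability alone. Here, among incompletely tested patients, inclusion depends on the result: every Yes stays and every No leaves. Even if testing has nothing to do with disability, the proportion must then exceed the true one whenever an incompletely tested patient is found to have progressed.

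A reader who sees a complete case label will take a gap between this result and the main one as evidence that missing optional tests matter clinically. Part or all of the gap may come from the inclusion rule. The analysis then cannot do the job 14.3.2 gives it, and it leaves the bias flagged in Protocol 9.7.3 in place.

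**Working it through.** The plan gives no figure to reproduce: it states no progression rate and no testing rate. The rules were applied as written over an assumed range.

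**Inputs**
- p: true proportion progressing on the three-test composite. Assumed 10%, with 20% as a variant.
- f: share with all three tests at both visits, unrelated to outcome. Assumed 30% and 70%.
- s: share of incompletely tested progressors detected on the tests they did have. Assumed 1, 0.5 and 0.
- All patients assessable. N = 242 enrolled (Protocol 9.5) where counts are used.

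**Formulas**
- Yes found, which is also the main result: Y = p[f + (1−f)s]
- First sensitivity analysis as written: Y / [Y + f(1−p)], because only completely tested No patients remain
- Symmetric complete case: pf / [pf + (1−p)f] = p for any f above 0
- NR for progression: 1 − (1−p)f, because only completely tested No patients stay No

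**Results at p = 10%**

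| f | s | Main (Y) | First analysis as written | Symmetric set |
|---|---|---|---|---|
| 30% | 1 | 10% | 0.100/(0.100+0.270) = 27% | 10% |
| 30% | 0.5 | 6.5% | 0.065/(0.065+0.270) = 19% | 10% |
| 30% | 0 | 3% | 0.030/(0.030+0.270) = 10% | 10% |
| 70% | 1 | 10% | 0.100/(0.100+0.630) = 14% | 10% |
| 70% | 0.5 | 8.5% | 0.085/(0.085+0.630) = 12% | 10% |
| 70% | 0 | 7% | 0.070/(0.070+0.630) = 10% | 10% |

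At p = 20%, f = 30%, s = 1, the result is 0.20/(0.20+0.24) = 45%.

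The s = 1 rows are a ceiling. Inflation above p disappears only at s = 0, when the available tests detect none of the incompletely tested progressors.

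**In counts** (p = 10%, f = 50%, s = 1). Of 242 patients, 24 are Yes and 218 No. Half of the No patients (109) are retained. The main result is 24/242 = 9.9% (95% Clopper-Pearson 6.5 to 14.4%). The first analysis gives 24/133 = 18.0% (11.9 to 25.6%).

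**NR for progression** (p = 10%). At f = 30%: 1 − 0.9×0.3 = 73%. At f = 70%: 1 − 0.9×0.7 = 37%. Neither depends on s. At s = 1 the distance from the main result is (1−p)(1−f), that is 63 and 27 percentage points, so it largely reflects the share of patients without all three tests.

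**The case against.** The strongest defence is that the rule follows from the endpoint. Progression needs only one of three components, so one positive test settles the matter, while a partial negative does not. The SAP says it will classify only patients whose status is certain, and it states the direction of the bias. The table adds to this: when s is below 1 the main analysis falls short of p, so the first analysis errs in the opposite direction.

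Most of this stands as an account of why the rule was written. It does not rescue the analysis as a complete case estimate. Certainty about individuals is not the same as an unbiased proportion: keeping the certain Yes and dropping the uncertain No selects on outcome. Stating the direction of a bias does not remove it or give its size.

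A reader might also infer that the NR rule for progression is equally wrong, because it turns a patient with a stable EDSS into a progressor. The documents do not support that. On a one-of-three endpoint, a stable EDSS without the other two tests does not establish a No. The main analysis gives such patients the favourable value and NR gives them the unfavourable one, which is a coherent worst-case bound. Limiting NR to patients with no evaluable component would remove that stress test. What can fairly be asked is that the result be called a bound and read beside the testing rate.

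**Conclusion.** The point holds for the first sensitivity analysis, for progression and improvement alike. Its denominator depends on the outcome, and its proportion is biased upward as optional testing falls. In the illustration it gives between 10% and 27% for a true 10% when 30% are fully tested, and between 10% and 14% when 70% are. These figures rest on assumed p, f and s and on testing being unrelated to outcome. The upward direction needs only that independence, some incomplete testing, and s above 0. EDSS is scheduled at every visit and is not optional, so s = 0 is unlikely.

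Three stronger conclusions are tempting but unsupported:

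- **That the first two analyses will land far from the main result whatever the truth.** The first gives 14% against 10% at f = 70% even at its ceiling, and both converge on the main result as f approaches 100%.
- **That the conversion of No to Yes affects improvement.** It applies to progression only.
- **That the disability results as a whole are compromised.** These are supportive analyses of a secondary endpoint. The main result is unchanged, and the EDSS-only analyses give a check that does not depend on the optional tests.

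**What to change.** - **SAP 14.3.2 and 14.4.2, first analysis.** Define the set as patients with EDSS, T25FW and 9HPT all recorded at both compared visits, and take both Yes and No from that set only.
- **SAP 14.3.2, NR analysis.** Keep the rule, but label and report it as a worst-case bound whose distance from the main result largely reflects the share without all three tests. A further version that imputes only patients with no evaluable component is optional.
- **Reporting.** Show test completion by visit beside these results, including the number with all three tests at both compared visits. The planned by-visit summaries give missing counts for each score but not this joint count.

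The cost is a few sentences of SAP text and some precision. With 242 patients and f = 30%, the set is about 0.3×242 = 73. At 10% progression a rough normal half-width is 1.96×√(0.09/73) = 6.9 percentage points, against 1.96×√(0.09/242) = 3.8 in the whole cohort. At f = 70% (about 169 patients) it is 1.96×√(0.09/169) = 4.5. The planned exact intervals will differ somewhat.

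The change removes the selection built into the rule. It does not remove bias from sites choosing whom to test, which is why completion should be reported alongside.

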## 14.3.3 Subgroup Analyses of the Secondary Outcome 6-month Disability Progression

The subgroup analyses will be performed on the secondary outcome assessment based on the FAS for all subgroup levels defined in IAP Section 8.2 "Subgroup definition and parametrization". All the subgroup analyses are exploratory and will be performed unstratified.

A bar plot with disability progression from Visit 1 to Visit 4 overall and by subgroup will be presented.

### 14.4 Secondary Outcome 6-month Disability Improvement

The percentage of patients with 6-month disability improvement at the end of the study follow-up period (2 years), measured as EDSS, T25FW (optional) and 9-HPT (optional).

Disability Improvement is defined as an improvement on  $\geq 1$  of 3 components (EDSS, T25FW, and/or 9HPT) confirmed  $\geq 24$  weeks apart and with a  $\geq 20\%$  minimum threshold change for T25FW and 9HPT. Improvement on EDSS is defined as a decrease in EDSS by at least 1 point (1.5 points if baseline EDSS was 1.5).

# 14.4.1 Secondary Objective: Derivation and analysis of the Secondary Outcome 6-month Disability Improvement

#### **Derivations**

Disability improvement will be assessed using the Visit 4 data and comparing the results with Visit 3. As per definition, if Visit 4 and Visit 3 dates are not separated by at least 24 weeks, disability improvement will be set to missing. Disability improvement will be assessed if at least one assessment (EDSS, T25FW or 9HPT) is available. As per definition, disability improvement will be derived as "Yes" if at least one of the below cases occur:

- Visit 4 EDSS is ≥1 point smaller than Visit 3 EDSS if Visit 3 EDSS is greater than 1.5;
- Visit 4 EDSS is 0 when Visit 3 EDSS is 1.5;
- 20% decrease in the T25FW score (average of the two trials) from Visit 3 to Visit 4;
- 20% decrease in the 9HPT score (The two trials for each hand are averaged, converted to the reciprocals of the mean times for each hand and then the two reciprocals are averaged) from Visit 3 to Visit 4.

If none of those cases occurred, disability improvement will be set to "No".

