8.2 Secondary Objectives

- To assess change in annualized relapse rate (ARR) in patients switching from first-line DMDs to Cladribine tablets, between the 12-month pre-baseline period and over the 12 months period after initiation of Cladribine tablets (1 year)
- To assess disability progression. Disability progression is defined as progression on ≥1 of 3 components (EDSS, T25FW, and/or 9HPT) confirmed ≥24 weeks apart and with a ≥20% minimum threshold change for T25FW and 9HPT. T25FW and 9HPT are optional and will be performed if done as per routine practice. Progression on EDSS is defined as at least 1 point in the EDSS score or an increase of at least 1.5 points if the baseline EDSS score is 0.
- To assess disability improvement. Disability Improvement is defined as improvement on ≥1 of 3 components (EDSS, T25FW, and/or 9HPT) confirmed ≥24 weeks apart and with a ≥20% minimum threshold change for T25FW and 9HPT. T25FW and 9HPT are optional and will be performed if done as per routine practice. Improvement on EDSS is defined as a decrease in EDSS by at least 1 point (1.5 points if baseline EDSS was 1.5).
- To assess safety of Cladribine tablets in the real world, at two years
- To assess Quality of Life and treatment satisfaction
- To assess treatment adherence

-

Exploratory Objectives

- For those patients that the treating physicians decide to prescribe an MRI at baseline and/or Year 2:
 - 1. To compare MRI characteristics between baseline and Years 1 and 2
 - To compare MRI characteristics between the 12-month pre-baseline and postbaseline results (Years 1 and 2)
- To study effectiveness in 5 subgroups, defined according to the pre-baseline DMD treatment (IFN- B 1a / IFN- B 1 B / Glatiramer Acetate, Teriflunomide, DMF).

L04AA40 MS700568_0070	Cladribine	
9	Research Methods	
9.1	Study Design	
9.1.1	Design Overview	

This is a prospective, non-interventional, multicenter, Phase IV study in patients with a confirmed diagnosis of RRMS who switched from first-line DMD treatment (Interferons, Glatiramer Acetate, Teriflunomide, DMF) to treatment with Cladribine tablets in routine clinical practice.

No study specific interventions will be performed on the patients and there will not be any study specified visits. Assessments planned in this protocol will be according to clinical practice.

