#### **Analysis methods**

No missing data imputation will be performed. The proportion of patients with 6-month disability improvement at the end of study will be presented including associated 95% Clopper Pearson exact intervals. Disability improvement at Visit 2 and Visit 3 will also be presented and derived in the same way as described for Visit 4.

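### The 6-month improvement percentage counts as 'No' patients whose reference EDSS leaves them no route to 'Yes', and the EDSS bullets leave out a reference score of 1.0 that the definition covers

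*SAP*

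**What the plan says.** SAP 14.4.1 fixes the reference visit: "Disability improvement will be assessed using the Visit 4 data and comparing the results with Visit 3". Results at Visits 2 and 3 are to be derived in the same way, which I read as each visit against the one before.

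The EDSS has two routes to 'Yes': "Visit 4 EDSS is ≥1 point smaller than Visit 3 EDSS if Visit 3 EDSS is greater than 1.5", and "Visit 4 EDSS is 0 when Visit 3 EDSS is 1.5". The other two routes are a 20% change in T25FW or in 9HPT between the same visits. Protocol 8.2 makes those tests discretionary: "T25FW and 9HPT are optional and will be performed if done as per routine practice".

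The entry condition is loose: "Disability improvement will be assessed if at least one assessment (EDSS, T25FW or 9HPT) is available". The default closes the rule: "If none of those cases occurred, disability improvement will be set to" 'No'. Under Analysis methods, "The proportion of patients with 6-month disability improvement at the end of study will be presented" with exact 95% limits, and nothing restricts it to patients who could improve.

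The definition in SAP 14.4, which repeats Protocol 8.2, is worded differently from the bullets: "Improvement on EDSS is defined as a decrease in EDSS by at least 1 point (1.5 points if baseline EDSS was 1.5". It sets no lower limit on the starting score other than the special case at 1.5.

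SAP 14.4.2 plans four sensitivity analyses: complete-case, non-responder, EDSS-only, and EDSS-only split by closeness to a relapse. SAP 14.4.3 plans a bar plot by visit, overall and by prior DMD.

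**The concern.** The 'No' category mixes two kinds of patient: those who could have improved and did not, and those for whom no result at Visit 4 could have counted. How many fall in the second group depends on how many patients sit at the bottom of the EDSS at the reference visit and on how many sites do T25FW and 9HPT routinely. Neither is a property of the treatment effect.

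Two prior-DMD subgroups, or two visits, could therefore show bars of different height with the same improvement rate among patients able to improve. A reader of the plots could not tell, because the plan does not report how many patients were unable to qualify.

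The score of 1.0 raises a separate problem. There the bullets and the definition disagree, so a patient who meets the definition can be recorded as not improved.

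**Working it through.** **1. Which reference scores can qualify on EDSS.** I take EDSS values as 0, 1.0, 1.5, 2.0 and upward in half points (an assumption about the scale; the documents do not list the values). Each Visit 3 score is run through the bullets in SAP 14.4.1 and the definition in SAP 14.4, with Visit 3 as reference in both.

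| Visit 3 EDSS | Visit 4 values giving 'Yes', bullets | Visit 4 values giving 'Yes', definition |
|---|---|---|
| 0 | none | none |
| 1.0 | none | 0 |
| 1.5 | 0 | 0 |
| 2.0 | 0, 1.0 | 0, 1.0 |
| 2.5 | 0, 1.0, 1.5 | 0, 1.0, 1.5 |

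Bullets and definition differ only at 1.0. At 0 neither gives a route. Without T25FW or 9HPT at both visits, a Visit 3 score of 0 or 1.0 is therefore always 'No' under the bullets.

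**2. Size of the dilution.** The documents state no expected improvement rate, EDSS distribution or testing rate, so there is no plan figure to reproduce and every input here is assumed. Let f be the share of assessed patients whose reference EDSS cannot qualify, u the share of those without an optional test at both visits, and p the improvement rate among patients able to qualify.

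- Structural 'No' share: s = f × u. With f = 10-30% and u = 50-80%, s runs from 0.10 × 0.5 = 5% to 0.30 × 0.8 = 24%.
- Percentage shown: p × (1 − s). With p = 15%: 15 × 0.95 = 14.25%, down to 15 × 0.76 = 11.4%.
- EDSS-only analysis, where u plays no part: 15 × 0.90 = 13.5%, down to 15 × 0.70 = 10.5%.
- Two subgroups at the ends of the first range would differ by 14.25 − 11.4 = 2.85 points with no difference in p.
- Over p = 5-20%, f = 5-30% and u = 20-100%, the gap p × f × u runs from 0.05 × 0.05 × 0.20 = 0.05 points to 0.20 × 0.30 × 1 = 6.0 points.

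In counts, using the planned enrolment of 242 (Protocol 9.5) as if all were assessed, with f = 20%, u = 100% and p = 10%: 48 cannot qualify, 194 can, and 19 improve. That is 19/242 = 7.9% (exact 95% CI 4.8-12.0) over all patients and 19/194 = 9.8% (6.0-14.9) among those able.

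**3. Whether the sensitivity analyses deal with it.**

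- *Complete-case.* A 'No' with only one or two tests becomes missing, so the affected patients leave the 'No' group. So does every EDSS-only 'No' patient who could have improved, while every 'Yes' stays. Let t be the share of patients with all three tests, the rest having EDSS only, with p = 10% among those able in both groups and f = 20%. If missing cases leave the denominator, the result is [p·t + p(1−t)(1−f)] / [t + p(1−t)(1−f)]. For t = 20%, 50% and 80% this is 0.084/0.264 = 31.8%, 0.090/0.540 = 16.7% and 0.096/0.816 = 11.8%, against 10% among patients able to qualify. SAP 14.4.2 itself expects this analysis to overestimate.
- *Non-responder.* These patients stay 'No'.
- *EDSS-only.* Every patient at reference EDSS 0 is a structural 'No', including those who had the optional tests.
- *Relapse-timing split.* It repeats the EDSS-only rule and inherits its floor.

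The denominator is also unsettled: SAP section 9 keeps missing cases in the denominator unless otherwise stated, while SAP 14.4.2 says the complete-case analysis includes fewer patients.

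**The case against.** The strongest reply is that the endpoint is a percentage of patients, not of patients able to improve. Someone who stays at EDSS 0 has not improved on EDSS, so 'No' is the right entry. That stands. A reader might infer that the planned percentage is biased downward because of EDSS 0; the documents do not support that. Converting 15% to 11.4% changes the denominator and does not correct an error. At EDSS 0, misclassification would need an optional test that was not done but would have shown improvement, and the figures above do not estimate that.

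A reader might also infer that patients who enter the study at EDSS 0 are shut out. The derivation does not support that either. Someone at 0 at study baseline and 2.0 at Visit 3 can qualify, while someone at 3.0 at baseline and 0 at Visit 3 cannot qualify on EDSS.

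It is also fair that Protocol 9.7.3 recognises possible bias from the optional tests, that the SAP responds with the complete-case and non-responder analyses and states their expected directions, and that the endpoint is descriptive, with exploratory subgroups and confirmatory testing on the primary outcome only. This limits the consequence. It does not supply an analysis that separates 'did not improve' from 'could not improve'.

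Finally, a denominator of patients able to qualify on any test still depends on who was tested, and patients with three tests have more routes to 'Yes' than patients with one. That stands, and it is why the fix includes an EDSS-only version.

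**Conclusion.** The point holds as one of floor dilution and interpretation, together with one plain inconsistency. Patients at reference EDSS 0 without an optional test at both visits cannot be 'Yes' but are counted, and no planned analysis isolates the patients able to improve. The all-patient percentage is valid as defined. It is lower than the percentage among patients able to improve by a proportion equal to the structural 'No' share, and that share can differ between visits and prior-DMD subgroups.

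At reference EDSS 1.0 the matter is firmer: a fall to 0 meets the definition in Protocol 8.2 and SAP 14.4 but fails the SAP 14.4.1 bullets. Since SAP section 7 declares no change from the protocol, the difference looks unintended.

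The size cannot be derived from the documents. The step from 15% to about 14.2-11.4% rests on assumed values for the share at the floor, the share untested and the improvement rate; the upper end combines the extremes of the first two. The change is worth making because it is cheap, although no confirmatory conclusion depends on it.

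**What to change.** 1. In SAP 14.4.1, align the EDSS bullets with the definition in SAP 14.4 so that a change from 1.0 to 0 is treated the same in both places.
2. Keep the all-patient percentage. Beside it report, with n and exact 95% CI, the percentage among patients able to meet at least one criterion: reference EDSS high enough for the required fall (1.0 or above once the bullets are aligned), or T25FW or 9HPT available at both visits. Give the number unable to qualify, and state the denominator of each row.
3. In the EDSS-only sensitivity analysis of SAP 14.4.2, add the percentage restricted to patients whose reference EDSS can fall by the required amount. This figure does not depend on optional testing; show it by prior-DMD subgroup next to the planned plot.

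The cost is one derived flag and a few table rows from data already collected. The downside is a smaller denominator and a slightly wider interval: in the worked example the exact CI goes from 4.8-12.0 (width 7.2 points) to 6.0-14.9 (width 8.9 points).

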## 7 Changes to the Planned Analyses in the Clinical Study Protocol

There are no changes to the analyses planned per protocol.

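### SAP 14.4.1 gives no EDSS improvement credit for a fall from 1.0 to 0, although the protocol and SAP 14.4 ask for more than one point only from a starting EDSS of 1.5

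*SAP*

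**What the plan says.** **Definition.** SAP 14.4 repeats the protocol (section 8.2 and the outcome footnotes): "Improvement on EDSS is defined as a decrease in EDSS by at least 1 point (1.5 points if baseline EDSS was 1.5". It makes a single exception, for a starting value of 1.5.

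**Derivation.** SAP 14.4.1 compares Visit 4 with Visit 3 and has two EDSS cases:
- A fall of one point or more counts, but only "if Visit 3 EDSS is greater than 1.5".
- From a starting value of exactly 1.5, only a fall all the way to 0 counts.

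Two further cases cover a 20% decrease in T25FW or 9HPT, both optional tests. A patient who meets none of the four is coded No. If Visits 3 and 4 are less than 24 weeks apart, the outcome is set to missing.

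**Status of the rule.** SAP 14.4.1 presents these cases as following the definition. SAP section 7 states: "There are no changes to the analyses planned per protocol".

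**The concern.** The definition carves out one starting value, 1.5. The derivation carves out everything at or below 1.5 and then restores only 1.5 itself. That leaves a starting value of 1.0 with no route to EDSS improvement, although a fall to 0 is a full point.

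The percentage of patients with 6-month disability improvement is a named secondary endpoint. The EDSS rule is also used beyond the Visit 4 result:
- Visits 2 and 3 are derived in the same way (SAP 14.4.1, analysis methods).
- The third and fourth sensitivity analyses use EDSS alone, and no separate EDSS rule is given for them (SAP 14.4.2).
- The prior-DMD subgroups use it (SAP 14.4.3).
- The interim improvement tables and bar plot use it (SAP 18.2).

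The EDSS-only analyses therefore cannot reveal the gap. T25FW and 9HPT are done only where they are routine, so for some patients EDSS may be the only component available.

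**Working it through.** **1. Definition against derivation.** Take Visit 3 as the starting value, as the derivation does, and assume EDSS in half-point steps from 0 to 10.

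| Visit 3 EDSS | Fall required by the definition | Visit 4 values that qualify by definition | Visit 4 values coded as EDSS improvement |
|---|---|---|---|
| 0 or 0.5 | 1 | none possible | none |
| 1.0 | 1 | 0 | **none** |
| 1.5 | 1.5 | 0 | 0 |
| 2.0 or more | 1 | all values at least 1 lower | the same |

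The two rules differ for exactly one pair on the grid: 1.0 to 0.

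**2. The progression rule as a comparator.** SAP 14.3 requires a 1-point rise, or 1.5 points from 0. SAP 14.3.1 codes "Visit 4 EDSS is ≥1 point greater than Visit 3 EDSS if Visit 3 EDSS is greater than 0" plus a separate case for 0. The same grid comparison gives no mismatch. The gap is specific to improvement.

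**3. Illustration of size.** The plan states no figure to reproduce. The inputs are:
- N = 242, planned enrolment (Protocol 9.5), used as the denominator.
- Share of patients at EDSS 1.0 at Visit 3: 5% to 15% (assumption).
- Probability of falling from 1.0 to 0 by Visit 4: 5% to 20% (assumption).

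Patients missed = N × share × probability.
- Low end: 242 × 0.05 × 0.05 = 0.6, about 1 patient.
- High end: 242 × 0.15 × 0.20 = 7.3, about 7 patients.

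With Clopper-Pearson 95% intervals, the method the SAP names, and two arbitrary derived counts:

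| As derived | Adding 1 | Adding 7 |
|---|---|---|
| 12/242 = 5.0% (2.6 to 8.5) | 13/242 = 5.4% (2.9 to 9.0) | 19/242 = 7.9% (4.8 to 12.0) |
| 24/242 = 9.9% (6.5 to 14.4) | 25/242 = 10.3% (6.8 to 14.9) | 31/242 = 12.8% (8.9 to 17.7) |

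In percentage points, share × probability runs from 0.05 × 0.05 = 0.25 to 0.15 × 0.20 = 3.0. If the probability were 30%, the top would be 0.15 × 0.30 = 4.5. For whatever inputs are assumed, the product is an upper bound. It does not remove patients who are coded Yes through T25FW or 9HPT, or those set to missing because their visits are too close together.

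**The case against.** The best counter-argument concerns the comparator. The definition speaks of baseline EDSS and of change confirmed at least 24 weeks apart, whereas the derivation compares two late visits. A reader might infer that this bullet loses every improved patient who started the study at EDSS 1.0. The documents do not support that, as two cases show:
- Baseline 1.0, Visit 3 at 0, Visit 4 at 0: coded No on EDSS with or without the correction, because Visit 4 equals Visit 3. The cause is the comparator, not this bullet.
- Baseline 0, Visit 3 at 1.0, Visit 4 at 0: the corrected bullet would code Yes, although the patient has not improved from baseline.

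This objection stands as a limit. The mismatch is established for the comparator the SAP uses, and correcting the bullet does not settle whether that comparator is the right one.

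Three other limits also stand. The definition does not count every one-point decrease, since 1.5 points are needed from 1.5. A patient going from 1.0 to 0 is not always coded No overall, because T25FW or 9HPT can give Yes and a short visit interval gives missing. And the outcome is secondary, reported as a proportion with an interval, while SAP section 9 confines confirmatory testing to the primary outcome.

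It could also be argued that leaving out 1.0 to 0 was deliberate. Nothing in the documents says so. The derivation claims to follow the definition, and section 7 declares no change. If the exclusion was intended, the definition would be the text that needs changing.

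**Conclusion.** The mismatch is real and narrow. As SAP 14.4.1 is written, a fall from 1.0 to 0 between the compared visits does not count as EDSS improvement, while the definition applied to the same visits counts it. No other section closes the gap. With visits at least 24 weeks apart, the patient is coded No unless T25FW or 9HPT falls by 20%.

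Relative to the definition on that comparator, the error can only undercount improvement. Its size is unknown: the documents give neither an EDSS distribution nor a transition rate, so the illustrated figures rest wholly on assumed inputs. A reader might infer a loss of several percentage points, but the documents do not support any particular figure. The primary ARR analysis is unaffected. The point merits correction because the rule contradicts its own definition and the repair is cheap, not because a large effect has been shown.

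**What to change.** Replace the first EDSS bullet in SAP 14.4.1 with: EDSS is at least 1 point lower than the comparator EDSS, for any comparator EDSS of 1.0 or more other than 1.5. Keep the 1.5-to-0 bullet. Apply the rule wherever EDSS improvement is derived: every visit reported, the EDSS-only analyses, the subgroups and the interim outputs.

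State in the same place that the comparator is the one the derivation uses, which for the Visit 4 result is Visit 3 as now written. Reconcile that choice with the definition's reference to baseline EDSS as a separate item, since the bullet alone cannot resolve it. If the sponsor does mean to exclude a fall from 1.0 to 0, amend the definition in the protocol and SAP 14.4 instead, and list the change in SAP section 7.

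The cost is one line in the SAP and one condition in the program, with no new data. Any interim improvement output already produced would need a rerun or a note. While Visit 3 remains the comparator, the correction can add a patient who has not improved from baseline, which is why the comparator has to be stated.
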